6.2. Exclusion Criteria

Subjects will be excluded from study enrollment if they meet any of the following criteria at screening and/or enrollment:

- [8] Are investigative site personnel directly affiliated with this study and their immediate families. Immediate family is defined as a spouse, biological or legal guardian, child, or sibling.
- [9] are Lilly employees
- [10] are currently enrolled in a clinical trial involving an investigational product or any other type of medical research judged not to be scientifically or medically compatible with this study
- [11] have participated, within the last 30 days, in a clinical trial involving an investigational product. If the previous investigational product has a long half-life, 3 months or 5 half-lives (whichever is longer) should have passed.
- [12] have previously completed or withdrawn from this study or any other study investigating baricitinib, and have previously received the investigational product
- [13] have known allergies to baricitinib, related compounds, or any components of the formulation, or history of significant atopy
- [14] have an abnormality in the 12-lead ECG that, in the opinion of the investigator, increases the risks associated with participating in the study
- [15] have an abnormal blood pressure as determined by the investigator
- [16] have a history of or current cardiovascular, respiratory, hepatic, renal, gastrointestinal, endocrine, hematological, or neurological disorders capable of significantly altering the absorption, metabolism, or elimination of drugs; of constituting a risk when taking the investigational product; or of interfering with the interpretation of data
- [17] have known or ongoing psychiatric disorders that would interfere with study participation as determined by the investigator
- [18] regularly use known drugs of abuse
- [19] show evidence of human immunodeficiency virus (HIV) infection and/or positive HIV antibodies
- [20] show evidence of hepatitis C and/or positive hepatitis C antibody
- [21] show evidence of hepatitis B and/or positive hepatitis B surface antigen
- [22] are women who are pregnant or lactating
- [23] have used or intend to use over-the-counter or prescription medication, including herbal medications, within 14 days prior to dosing and during the study

- [24] have donated blood of more than 450 mL within 3 months of study enrollment
- [25] have an average weekly alcohol intake that exceeds 21 units per week (males) and 14 units per week (females), or are unwilling to abide by alcohol restrictions as specified in Section 6.3.2 (1 unit = 12 oz or 360 mL of beer; 5 oz or 150 mL of wine; 1.5 oz or 45 mL of distilled spirits)
- [26] are subjects who currently smoke more than 10 cigarettes per day (or equivalent in tobacco or nicotine products) or are unwilling to abide by smoking restrictions as specified in Section 6.3.2
- [27] have a current or recent history (<30 days prior to screening and/or <45 days prior to Day -1 in Period 1) of a clinically significant bacterial, fungal, parasitic, viral (not including rhinopharyngitis), or mycobacterial infection
- [28] have an ANC <2000 cells/ μ L ($2 \times 10^9/L$) at screening. For abnormal values, a single repeat will be allowed.
- [29] have had symptomatic herpes zoster within 3 months of screening
- [30] have received live vaccine(s) within 3 months of screening, or intend to during the study
- [31] are unwilling to comply with the dietary requirements/restrictions during the study: (i) consume only the meals provided during inpatient visits (see Section 6.3), and (ii) refrain from consuming grapefruit, star fruit, pomelos, or products containing these fruits, for at least 14 days prior to the first dose and during the study
- [32] have used or intend to use drugs or substances that are known to be strong or moderate inhibitors or inducers of cytochrome P450 (CYP) 3A or strong inhibitors of organic anion transporter 3 (OAT3; such as probenecid) within 30 days prior to the first dose and throughout the study
- [33] Have a history of, in the opinion of the investigator, excessive methylxanthine use within the previous 6 months, or are unwilling to abide by restrictions as specified in Section 6.3.2. Excessive intake is defined as more than 6 units of caffeine per day; one caffeine unit is contained in the following items: 1 (177 mL) cup of coffee, 1 (355 mL) cup of tea, 2 (355 mL) cans of cola, or 3 oz (85 g) of chocolate.
- [34] in the opinion of the investigator or sponsor, are unsuitable for inclusion in the study

6.3. Lifestyle and/or Dietary Requirements

Throughout the study, subjects may undergo medical assessments and review of compliance with requirements before continuing in the study.

6.3.1. Meals and Dietary Restrictions

Grapefruit, star fruit, pomelos, or products containing these fruits will not be allowed from 14 days prior to the first dose and during the study.

Administration of baricitinib in the fasted state

Following an overnight fast (water only permitted) of at least 10 hours, subjects will be administered 4 mg baricitinib with or without approximately 240 mL room temperature water (as determined by the randomization schedule [Part A] or based on the results from the interim analysis planned for Part A [Part B]). Water can be allowed as desired except from 1 hour before until 2 hours after drug administration. No food or fluid (except water) will be allowed for at least 4 hours postdose. Lunch will be provided after the 4-hour PK sample is collected.

Administration of baricitinib in the fed state (Part B only)

Following an overnight fast (water only permitted) of at least 10 hours, subjects will start a US FDA-defined high-fat, high-calorie meal 30 minutes prior to administration of baricitinib. It is intended that the meal will be ingested in its entirety over an approximate 25-minute period, such that it is completed at least 5 minutes before dosing. A 4-mg dose of baricitinib will be given with or without approximately 240 mL room temperature water (as determined by interim analysis of data from Part A). Water can be given as desired except for 1 hour before and 2 hours after drug administration. No further food or fluids (except water) will be permitted until at least 4 hours postdose and lunch will be provided after collection of the 4-hour PK sample.

High-fat meal: The high-fat, high-calorie meal (fat comprises approximately 50% of total calorific content) should consist of approximately 800 to 1000 kilocalories in total. No additional food or substitute is allowed. A typical test meal is 2 eggs fried in butter, 2 strips of bacon, 2 slices of toast with butter, 4 ounces of hash brown potatoes, and 8 ounces of whole milk. The test meal derives approximately 150, 250, and 500 to 600 kilocalories from protein, carbohydrate, and fat, respectively.

6.3.2. Caffeine, Alcohol, and Tobacco

Alcohol – Alcohol will not be permitted from 48 hours prior to each admission until after collection of the 48-hour PK sample in each period and within 48 hours prior to the follow-up visit. During the washout period, alcohol will be restricted to a maximum of 2 units per day.

Caffeine/methylxanthine – Subjects will be advised not to exceed their usual intake of caffeine- or methylxanthine-containing food and drinks, such as coffee, tea, cola, and chocolate during the study.

Smoking – Subjects should not smoke or use any nicotine products from 2 hours prior to each admission until after collection of the 48-hour PK sample.

6.3.3. Activity

Subjects should not engage in strenuous physical exercise from 1 week prior to the first dose until completion of the follow-up assessments.

6.4. Screen Failures

Individuals who do not meet the criteria for participation in this study (screen failure) may be rescreened. Individuals may be rescreened only once, at the discretion of the investigator. The interval between rescreenings should be at least 1 week. If rescreening is performed, the individual must sign a new informed consent form (ICF) and will be assigned a new identification number.

7. Treatment

7.1. Treatment Administered

Part A of this study involves a comparison of baricitinib administered as a 4-mg dose of the suspension formulation administered with and without 240 mL water with baricitinib administered as a 4-mg dose of the commercial tablet formulation administered with 240 mL water.

Table JAGU.4 shows the treatment regimens for Part A.

Baricitinib will be administered orally as 1×4 -mg tablet with approximately 240 mL room temperature water, as $2 \text{ mL} \times 2 \text{ mg/mL}$ suspension administered without water, or as $2 \text{ mL} \times 2 \text{ mg/mL}$ suspension followed immediately by 240 mL of room temperature water, in the morning of Day 1 of the appropriate treatment period (as defined by the randomization). Subjects will not be allowed to lie supine for 2 hours after dosing, unless clinically indicated or for study procedures.

Table JAGU.4. Treatments Administered in Part A

Treatment name	Baricitinib	Baricitinib	Baricitinib
Dosage formulation	Suspension	Suspension	Commercial Tablet
Dosage level(s)/ Unit dose strengths	$2 \text{ mL} \times 2 \text{ mg/mL}$	$2 \text{ mL} \times 2 \text{ mg/mL}$	$1 \times 4\text{-mg}$
Route of administration	Oral	Oral	Oral
Dosing instructions^a	Dose administered following ≥ 10 -hour fast without water	Dose administered following ≥ 10 -hour fast and immediately prior to 240 mL water	Dose administered following ≥ 10 -hour fast with 240 mL water

^a Further instructions for the storage and dispensing of the suspension formulation will be provided to the site in a separate document.

Part B of this study involves a comparison of baricitinib administered as a 4-mg dose of the suspension formulation in the fasted state compared to following a high-fat, high-calorie meal.

A 4-mg dose of baricitinib will be administered orally as $2 \text{ mL} \times 2 \text{ mg/mL}$ suspension in the morning of Day 1 of each treatment period. Whether the doses are administered alone or followed by 240 mL room temperature water will be subject to a decision based on interim analysis of data from Part A of the study (see Section 10.3.3). Subjects will not be allowed to lie supine for 2 hours after dosing, unless clinically indicated or for study procedures.

The investigator or designee is responsible for:

- explaining the correct use of the investigational products to the site personnel
- verifying that instructions are followed properly
- maintaining accurate records of investigational product dispensing and collection
- and returning all unused medication to Lilly or its designee at the end of the study

Note: In some cases, sites may destroy the material if, during the investigative site selection, the evaluator has verified and documented that the site has appropriate facilities and written procedures to dispose of clinical trial materials.

7.1.1. Packaging and Labeling

Each tablet of baricitinib contains 4 mg of active ingredient, and is provided as bulk supply in high-density polyethylene bottles.

Baricitinib suspension formulation contains 2 mg/mL baricitinib and is provided as bulk supply in polyethylene terephthalate bottles.

Clinical trial materials will be labeled according to the country's regulatory requirements.

7.2. Method of Treatment Assignment

Subjects will be randomized to treatment sequences using a computer-generated allocation schedule.

7.2.1. Selection and Timing of Doses

This study will use a fixed dose of 4 mg baricitinib. A dose of 4 mg is selected as it is the primary dose studied in Phase 3 clinical studies and is the recommended commercial dose in patients with RA.

The doses will be administered at approximately the same times on each day. The actual time of all dose administrations will be recorded in the subject's electronic case report form (eCRF).

7.3. Blinding

This will be an open-label study.

7.4. Dose Modification

Dose reductions or adjustments will not be allowed during this study.

7.5. Preparation/Handling/Storage/Accountability

Only participants enrolled in the study may receive investigational product and only authorized site staff may supply or administer study treatment. All study treatments should be stored in an environmentally controlled and monitored (manual or automated) area in accordance with the labeled storage conditions with access limited to the investigator and authorized site staff.

Baricitinib tablets and suspension will be stored at room temperature.

The investigator, institution, or the head of the medical institution (where applicable) is responsible for study treatment accountability, reconciliation, and record maintenance (such as receipt, reconciliation, and final disposition records).

7.6. Treatment Compliance

The investigational product will be administered at the clinical site, and documentation of treatment administration will occur at the site.

7.7. Concomitant Therapy

Over-the-counter or prescription medications, including herbal medications, are to be avoided within 14 days prior to dosing and during the study. Drugs that are known to be strong or moderate inhibitors or inducers of CYP3A or strong inhibitors of OAT3 (such as probenecid) are not allowed within 30 days prior to the first dose and throughout the study. Additional drugs are to be avoided during the study unless required to treat an AE or for the treatment of an ongoing medical problem.

If the need for concomitant medication arises, inclusion or continuation of the subject may be at the discretion of the investigator after consultation with a Lilly clinical pharmacologist (CP) or clinical research physician (CRP). Any additional medication used during the course of the study must be documented.

7.8. Treatment After the End of the Study

This section is not applicable for this study.

8. Discontinuation Criteria

8.1. Discontinuation from Study Treatment

Subjects who discontinue the investigational product early will have early discontinuation procedures performed as shown in the Schedule of Activities (Section 2).

8.1.1. Discontinuation of Inadvertently Enrolled Subjects

If the sponsor or investigator identifies a subject who did not meet enrollment criteria and was inadvertently enrolled, the subject will be discontinued from the study and early discontinuation assessments will be performed as shown in the Schedule of Activities (Section 2).

8.2. Discontinuation from the Study

Subjects will be discontinued in the following circumstances:

- enrollment in any other clinical trial involving an investigational product or enrollment in any other type of medical research judged not to be scientifically or medically compatible with this study
- participation in the study needs to be stopped for medical, safety, regulatory, or other reasons consistent with applicable laws, regulations, and good clinical practice (GCP)
- investigator decision
 - the investigator decides that the subject should be discontinued from the study
- subject decision
 - the subject requests to be withdrawn from the study

Subjects who discontinue the study early will have early discontinuation procedures performed as shown in the Schedule of Activities (Section 2).

8.3. Subjects Lost to Follow-up

A subject will be considered lost to follow-up if he or she repeatedly fails to return for scheduled visits and is unable to be contacted by the study site. Site personnel are expected to make diligent attempts to contact subjects who fail to return for a scheduled visit or were otherwise unable to be followed up by the site.

9. Study Assessments and Procedures

Section 2 lists the Schedule of Activities, detailing the study procedures and their timing.

Appendix 2 lists the laboratory tests that will be performed for this study.

Appendix 4 provides a summary of the maximum number and volume of invasive samples, for all sampling, during the study.

Unless otherwise stated in subsections below, all samples collected for specified laboratory tests will be destroyed within 60 days of receipt of confirmed test results. Certain samples may be retained for a longer period, if necessary, to comply with applicable laws, regulations, or laboratory certification standards.

Investigators must document their review of each laboratory safety report.

9.1. Efficacy Assessments

This section is not applicable for this study.

9.2. Adverse Events

Investigators are responsible for monitoring the safety of subjects who have entered this study and for alerting Lilly or its designee to any event that seems unusual, even if this event may be considered an unanticipated benefit to the subject.

The investigator is responsible for the appropriate medical care of subjects during the study.

The investigator remains responsible for following, through an appropriate health care option, AEs that are serious or otherwise medically important, considered related to the investigational product or the study, or that caused the subject to discontinue the investigational product before completing the study. The subject should be followed until the event resolves, stabilizes with appropriate diagnostic evaluation, or is reasonably explained. The frequency of follow-up evaluations of the AE is left to the discretion of the investigator.

After the ICF is signed, study site personnel will record, via eCRF, the occurrence and nature of each subject's preexisting conditions. Additionally, site personnel will record any change in the condition(s) and the occurrence and nature of any AEs.

The investigator will interpret and document whether or not an AE has a reasonable possibility of being related to study treatment, or a study procedure, taking into account concomitant treatment or pathologies.

A "reasonable possibility" means that there is a cause and effect relationship between the investigational product and/or study procedure and the AE.

Planned surgeries should not be reported as AEs unless the underlying medical condition has worsened during the course of the study.

If a subject's investigational product is discontinued as a result of an AE, study site personnel must report this to Lilly or its designee via eCRF.

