9.2.1. Serious Adverse Events

An SAE is any AE from this study that results in one of the following:

- death
- initial or prolonged inpatient hospitalization
- a life-threatening experience (that is, immediate risk of dying)
- persistent or significant disability/incapacity
- congenital anomaly/birth defect
- events considered significant by the investigator based upon appropriate medical judgment

Study site personnel must alert Lilly, or its designee, of any SAE within 24 hours of investigator awareness of the event via a sponsor-approved method. If alerts are issued via telephone, they are to be immediately followed with official notification on study-specific SAE forms. This 24-hour notification requirement refers to the initial SAE information and all follow-up SAE information.

Although all AEs are recorded in the eCRF after signing informed consent, SAE reporting begins after the subject has signed informed consent and has received investigational product.

However, if an SAE occurs after signing informed consent, but prior to receiving investigational product, AND is considered reasonably possibly related to a study procedure then it MUST be reported.

Investigators are not obligated to actively seek AEs or SAEs in subjects once they have discontinued from and/or completed the study (the subject summary eCRF has been completed). However, if the investigator learns of any SAE, including a death, at any time after a subject has been discharged from the study, and he/she considers the event reasonably possibly related to the study treatment or study participation, the investigator must promptly notify Lilly .

Pregnancy (maternal or paternal exposure to investigational product) does not meet the definition of an AE. However, to fulfill regulatory requirements any pregnancy should be reported following the SAE process to collect data on the outcome for both mother and fetus.

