9.2.1.1. Suspected Unexpected Serious Adverse Reactions

Suspected unexpected serious adverse reactions (SUSARs) are serious events that are not listed in the IB and that the investigator identifies as related to investigational product or procedure. United States 21 Code of Federal Regulations 312.32 and European Union Clinical Trial Directive 2001/20/EC and the associated detailed guidances or national regulatory requirements in participating countries require the reporting of SUSARs. Lilly has procedures that will be followed for the recording and expedited reporting of SUSARs that are consistent with global regulations and the associated detailed guidances.

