10.3.1. Safety Analyses

10.3.1.1. Clinical Evaluation of Safety

All investigational product and protocol procedure AEs will be listed, and if the frequency of events allows, safety data will be summarized using descriptive methodology.

The incidence of symptoms for each treatment will be presented by severity and by association with investigational product as perceived by the investigator. Symptoms reported to occur prior to study entry will be distinguished from those reported as new or increased in severity during the study. Each symptom will be classified by the most suitable term from the medical regulatory dictionary.

The number of investigational product-related SAEs will be reported.

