9.4.1 Adverse events

Where changes in severity are recorded in the Case Report Form (CRF), each separate severity of the AE will be reported in the listings, only the most severe will be used in the summary tables. A pre-existing condition is defined as an AE that starts before the subject has provided written informed consent and is ongoing at consent. A non-treatment emergent AE is defined as an AE which starts after informed consent but prior to dosing. A treatment-emergent AE is defined as an AE which occurs postdose or which is present prior to dosing and becomes more severe postdose.

All AEs will be listed. Treatment-emergent AEs will be summarized by treatment, severity and relationship to the study drug. The frequency (the number of AEs, the number of subjects experiencing an AE and the percentage of subjects experiencing an AE) of treatment-emergent AEs will be summarized by treatment, Medical Dictionary for Regulatory Activities (MedDRA) version 19.1 system organ class and preferred term. The summary and frequency AE tables will be presented for all causalities and those considered related to the study drug. Any serious AEs will be tabulated. Concomitant medication

Concomitant medication will be coded using the World Health Organization (WHO) drug dictionary (Version September 2016). Concomitant medication will be listed.

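### Protocol Section 9.2 defines a reasonable possibility of relatedness as actual causation, so applied literally it could under-record related events in the outputs and rules that use that judgement

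*Protocol*

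**What the plan says.** Protocol Section 9.2 has the investigator document "whether or not an AE has a reasonable possibility of being related to study treatment, or a study procedure", allowing for other treatments and conditions. The sentence that follows explains the key phrase: a reasonable possibility "means that there is a cause and effect relationship between the investigational product and/or study procedure and the AE". It carries no qualifier such as may, could or suspected.

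Later text relies on that judgement:

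- Section 9.2.1, for an SAE between consent and first dose, makes reporting conditional: "AND is considered reasonably possibly related to a study procedure then it MUST be reported". It uses the same possibly-related wording for an SAE that the investigator learns of after discharge, there in relation to study treatment or participation.
- Section 9.2.1.1 limits SUSARs to unlisted serious events "that the investigator identifies as related to investigational product or procedure".
- Section 10.3.1.1 states: "The number of investigational product-related SAEs will be reported".
- SAP Section 9.4.1 has the AE summary and frequency tables "presented for all causalities and those considered related to the study drug".

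The main SAE rule in Section 9.2.1 carries no causality condition: "Study site personnel must alert Lilly, or its designee, of any SAE within 24 hours of investigator awareness of the event".

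**The concern.** The definition does not match the term it defines. A reasonable possibility is a threshold of suspicion, whereas an existing cause and effect relationship is a finding of fact. The two give different answers for the ordinary case, an event that the drug may have caused but that has other plausible explanations.

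The design makes this case common. All treatments are active baricitinib, given as single doses with no placebo period, so causation can rarely be established for an individual event. An investigator who followed the sentence as written would have to answer no for many events that deserve a yes. Because the study has a single center, one site's reading would shape the whole related-event dataset, with no other site to show up the difference.

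At stake are the outputs and reporting rules that use the relatedness answer, above all SUSAR identification and the notification of SAEs learned of after discharge.

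**Working it through.** No formula applies, since the point concerns wording and the plan gives no figure to reproduce. The check has four steps.

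**1. Compare question and definition.** The question in Protocol 9.2 is about a possibility. The definition in the same section requires that the relationship exists. Section 9.2.1 twice speaks of events that are possibly related, and Section 9.2.1.1 concerns reactions that are by name suspected. Both presuppose suspicion, not proof, so the definition disagrees with its own term and with both of these sections.

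**2. Look for another definition.** Protocol Appendix 1 defines AE and TEAE, and says that neither needs a causal link to treatment, but it does not define relatedness. SAP 9.4.1 uses relationship to study drug without defining it. Section 9.2 is therefore the only definition in the two documents.

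**3. Trace where the judgement is used and where it is not.**

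| Item | Place | Depends on relatedness? |
|---|---|---|
| Drug-related AE tables | SAP 9.4.1 | Yes |
| Count of product-related SAEs; symptom incidence by association with product | Protocol 10.3.1.1 | Yes |
| SUSAR identification | Protocol 9.2.1.1 | Yes, through the investigator's answer |
| SAE before first dose | Protocol 9.2.1 | Yes, to a study procedure only |
| SAE learned of after discharge | Protocol 9.2.1 | Yes |
| AE follow-up duty | Protocol 9.2 | In part: relatedness is one of several alternative triggers |
| 24-hour alert for on-study SAEs after dosing | Protocol 9.2.1 | No |
| All-causality AE tables and AE listings | SAP 9.4.1 | No |
| TEAE incidence endpoint | Protocol objectives and endpoints table; Appendix 1 | No |
| Bioequivalence and food-effect analyses | Protocol 10.3.2; SAP 9.3 | No |

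**4. Direction and size.** Every event with an established cause and effect relationship also has a reasonable possibility of one, but not the reverse. Moving from the second standard to the first can therefore only leave the number of related events unchanged or lower it. By how much cannot be derived, because the documents give neither expected AE rates nor the split between possible and established causation. For context, planned enrollment gives 26 × 3 = 78 exposures in Part A and 18 × 2 = 36 in Part B, 114 in all and none on placebo. The Part B number may change after the interim analysis. This figure describes the setting and does not measure misclassification.

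**The case against.** The strongest reply is that no sensible investigator would apply the sentence literally. The question actually put is still about a possibility, Section 9.2.1 repeats that wording, and Section 10.3.1.1 reports association as the investigator perceives it. In context the sentence can be read as a reasonable possibility that a causal relationship exists. The literal reading would leave the question with almost no positive answers, which is itself a reason to doubt that it was meant. This stands to the extent that misclassification is a risk and not a certainty. It does not make the wording right, because the sentence is the only definition available and says something else.

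A second reply is that the sponsor has safeguards. Section 9.2.1.1 commits it to SUSAR procedures in line with global regulations, and Section 9.4.4 has sponsor physicians monitor safety data and review SAEs. These reduce the risk for on-study events, which the sponsor will hold in any case. They do not correct the definition, and Section 9.2.1.1 still makes SUSAR status turn on the investigator's answer. They also do not help with a post-discharge SAE judged unrelated, for which the protocol imposes no duty to notify.

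Two stronger readings are tempting. A reader might infer that possibly related SAEs would escape reporting in general. The documents do not support this, because any on-study SAE after dosing must be alerted whatever its cause. The pre-dose rule cannot lose a drug-related event either, since no drug has yet been given. A reader might also infer that the secondary tolerability objective is compromised. It is not: its endpoint is TEAE incidence regardless of cause, and all AEs are listed.

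**Conclusion.** The definition is wrong as written and should be corrected. Read literally, it sets a causation standard where the protocol intends a possibility standard, and could lead to possibly related events being recorded as unrelated. The reach is limited to the related-event summaries, SUSAR identification, the two conditional SAE rules and, in part, the AE follow-up duty.

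The conclusion assumes that the investigator applies the sentence as worded and that no eCRF guidance or training, neither of which is in the documents, overrides it. A claim that the related-AE tables will be biased to any stated degree would go beyond the documents, since any such figure would rest on invented proportions.

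**What to change.** Reword the sentence in Protocol 9.2 so that it expresses a possibility and agrees with 9.2.1, for example: *A reasonable possibility means that there are facts or arguments suggesting that the investigational product or a study procedure may have caused the AE; a cause and effect relationship need not be established.* State that this meaning governs Sections 9.2.1, 9.2.1.1 and 10.3.1.1 and SAP 9.4.1.

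Record relatedness to the investigational product and relatedness to study procedures as two separate answers. The present sentence joins them, while the SAP tables concern study drug and the SAE count in 10.3.1.1 concerns the product. With one combined answer, an effect of venipuncture could be counted as drug-related. Only the product answer should feed the drug-related tables and the product-related SAE count. The procedure answer serves the pre-dose SAE rule, and either answer can serve the SUSAR and post-discharge rules, as those sections are worded.

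The cost is one protocol sentence, matching eCRF instructions and, if the eCRF does not already separate the two, one extra field. No subjects, visits or procedures are added. The downside is that a few more events may be labelled related and possibly an extra report sent.
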